7.7.2.2. Reporting Other Special Situations

All other special situation reports must be reported on the special situations report form and forwarded to Gilead DSPH within 24 hours of the investigator becoming aware of the situation. These reports must consist of situations that involve study drug and/or Gilead concomitant medications, but do not apply to non-Gilead concomitant medications.

Special situations involving non-Gilead concomitant medications does not need to be reported on the special situations report form; however, for special situations that result in AEs due to a non-Gilead concomitant medication, the AE should be reported on the AE form.

Any inappropriate use of concomitant medications prohibited by this protocol should not be reported as “misuse,” but may be more appropriately documented as a protocol deviation.

Refer to Section 7.3 and the CRF/eCRF completion guidelines for full instructions on the mechanism of special situations reporting.

All clinical sequelae in relation to these special situation reports will be reported as AEs or SAEs at the same time using the AE CRF/eCRF and/or the SAE report form. Details of the symptoms and signs, clinical management, and outcome will be reported, when available.

8. STATISTICAL CONSIDERATIONS

8.1. Analysis Objectives and Endpoints

8.1.1. Analysis Objectives

The primary objective of this study is as follows:

- To evaluate the effect of GS-5745 on pre-bronchodilator FEV₁ % predicted in subjects with CF after 8 weeks of treatment

The secondary objectives of this study are as follows:

- To assess safety, tolerability, and PK of GS-5745 in subjects with CF
- To evaluate the effect of GS-5745 on post-bronchodilator FEV₁ % predicted in subjects with CF after 8 weeks of treatment

Exploratory objectives of this study are as follows:

- [REDACTED]
- [REDACTED]
- [REDACTED]
- [REDACTED]
- [REDACTED]
- [REDACTED]
- [REDACTED]

8.1.2. Primary Endpoint

- The absolute change in pre-bronchodilator FEV₁ percent predicted from Baseline to Week 8

8.1.3. Secondary Endpoints

8.1.3.1. Efficacy Endpoints

- The absolute change in post-bronchodilator FEV₁ percent predicted from Baseline to Week 8
- The relative change in pre-bronchodilator FEV₁ percent predicted from Baseline to Week 8
- The relative change in post-bronchodilator FEV₁ percent predicted from Baseline to Week 8

8.1.3.2. Safety Endpoints

The safety evaluation will be assessed by AEs, concomitant medications, clinical laboratory tests, vital signs and ADA data.

8.1.3.3. Pharmacokinetic Endpoints

Primary PK parameters will include C_{max}, T_{max}, C_{last}, T_{last}, and AUC_{last} (as applicable)

8.1.4. Other Endpoints of Interest

- Changes from Baseline in total and free MMP9 concentration and enzyme activity in sputum and/or blood
- Change from Baseline in FRI
- Change from Baseline in CFQ-R-RSS
- Change from Baseline in TSQM
- Change from Baseline in SNOT-22 score
- Change from Baseline in body weight
- Change from Baseline in sputum bacterial CFUs
- Change from Baseline in other biomarkers related to MMP9 pathway
- Change from Baseline in sputum cytology
- Rate of pulmonary exacerbations

8.2. Analysis Conventions

8.2.1. Analysis Sets

8.2.1.1. Efficacy

The primary analysis set for efficacy analysis is defined as the Full Analysis Set (FAS), which includes all subjects who were randomized into the study and received at least 1 dose of study drug.

Subjects will be analyzed according to the treatment group to which they are randomized.

8.2.1.2. Safety

The primary analysis set for safety analyses is the Safety Analysis Set. The Safety Analysis Set includes all subjects who received at least 1 dose of study drug.

Subjects will be analyzed according to the treatment they actually receive.

8.2.1.3. Pharmacokinetics

The PK Analysis Set includes all subjects who were randomized and have received at least 1 dose of study drug and for whom concentration data of GS-5745 are available.

Subjects will be analyzed according to the treatment they actually receive.

8.2.1.4. Biomarkers

The Biomarker Analysis Set includes all subjects who were randomized and have received at least 1 dose of study drug and for whom biomarker data are available.

Subjects will be analyzed according to the treatment they actually receive.

8.3. Data Handling Conventions

Values for missing safety laboratory data will not be imputed. However, a missing Baseline result will be replaced with a screening result, if available. If no pre-treatment laboratory value is available, the Baseline value will be assumed to be normal (ie, no grade [Grade 0]) for the summary of graded laboratory abnormalities. If safety laboratory results for a subject are missing for any reason at a time point, the subject will be excluded from the calculation of summary statistics for that time point.

Values for missing vital signs data will not be imputed. However, a missing Baseline result will be replaced with a screening result, if available.

8.4. Demographic Data and Baseline Characteristics

Demographic and Baseline measurements will be summarized using standard descriptive methods for continuous variables and number and percentage of subjects for categorical variables.

Demographic summaries will include sex, race/ethnicity, and age. Baseline data will include a summary of body weight, height, BMI, spirometry measurements, patient-reported outcome scores. Additional Baseline characteristic variables may be added if necessary.

8.5. Efficacy Analysis

The primary endpoint, the absolute change in pre-bronchodilator FEV₁ percent predicted from Baseline to Week 8, will be analyzed using a mixed effect model for repeated measure (MMRM) for Part 1 and Part 2 respectively. The model for each part of the study will include treatment, Baseline FEV₁ percent predicted level, visit and treatment-by-visit interaction as fixed effect, and subject as a random effect. Estimated least square means of treatment effects and estimated differences in treatment effects between GS-5745 treatment group and placebo group at Week 8 will be presented with the 90% confidence intervals (CIs) and adjusted p-values.

Analyses of absolute change in post-bronchodilator percent predicted FEV₁, relative change in pre and post -bronchodilator percent predicted FEV₁ and other endpoints listed in Section 8.1.4 will be discussed in the statistical analysis plan (SAP). In general, continuous endpoints with repeated measures will be analyzed using the MMRM model. For change in FRI and SNOT-22, an ANCOVA model with corresponding baseline values as covariate will be used. Categorical endpoints will be analyzed using MMRM and non-parametric tests. All endpoints will be summarized using descriptive statistics (n, mean, standard deviation [SD], median, Q1, Q3, minimum, and maximum) for continuous data and by the number and percent of subjects for categorical data.

8.6. Safety Analysis

Safety endpoints will be analyzed by the number and percentage of subjects for categorical variables or 8-number summary (n, mean, standard deviation, median, first quartile [Q1], third quartile [Q3], minimum, and maximum) for continuous variables.

All data collected during the course of study will be included in data listings. Additional details will be provided in the SAP.

8.6.1. Extent of Exposure

A subject's extent of exposure to study drug will be generated from the study drug administration and study drug accountability eCRF pages. The number of doses administered and the level of adherence will be summarized.

8.6.2. Adverse Events

Adverse events will be coded using the Medical Dictionary for Regulatory Activities (MedDRA). System Organ Class (SOC), High-Level Group Term (HLGT), High-Level Term (HLT), Preferred Term (PT), and Lower-Level Term (LLT) will be attached to the clinical database.

Treatment-emergent adverse events (TEAEs) are defined as 1 or both of the following:

- Any AEs with an onset date on or after the study drug start date and no later than 30 days after permanent discontinuation of study drug.
- Any AEs leading to premature discontinuation of study drug.

Summaries (number and percentage of subjects) of TEAEs by SOC and PT will be provided. Treatment-emergent AEs will also be summarized by relationship to study drug and severity. In addition, TEAEs leading to premature discontinuation of study drug and study will be summarized and listed.

8.6.3. Laboratory Evaluations

Selected laboratory data (using conventional units) will be summarized using only observed data. Data and change from Baseline at all scheduled time points will be summarized.

Graded laboratory abnormalities will be defined using the grading scheme in Section 7.5.

Incidence of treatment-emergent laboratory abnormalities, defined as values that increase at least one toxicity grade from Baseline at any time post Baseline will be summarized. If Baseline data are missing, then any graded abnormality (ie, at least a Grade 1) will be considered treatment emergent.

8.6.4. Other Safety Evaluations

Individual data for physical examination findings, prior and concomitant medications and medical history will be provided. Vital signs measurements will be listed by subject and summarized by incidence of events/abnormalities or descriptive statistics as appropriate.

8.7. Pharmacokinetic Analysis

The plasma concentration data of GS-5745 will be summarized by nominal sampling time and treatment using descriptive statistics (ie, n, arithmetic mean, geometric mean, coefficient of variation (%), standard deviation, median, minimum, and maximum). For the PK substudy, PK parameters (C_{max} , T_{max} , C_{last} , T_{last} , and AUC_{last} , as applicable) may be listed and summarized using descriptive statistics. Plasma concentrations over time may also be plotted in semi-logarithmic and linear formats as mean \pm standard deviation, and median (Q1, Q3) for PK sub-study. Exposure-response analysis may be performed.

8.8. Immunogenicity Analysis

Immunogenicity of GS-5745 will be evaluated based upon the incidence of anti-drug (GS-5745) antibody (ADA) formation. The number and percentage of subjects exhibiting positive ADA results at each specified time point will be summarized. ADA results with supporting data will be included in a listing as well. Impact of ADA on GS-5745 PK, safety, and efficacy will also be evaluated as applicable.

8.9. Biomarker Analysis

The changes from Baseline at Week 8 in total and free MMP9 and MMP9 activity in sputum and blood will be analyzed using an analysis of variance model or a mixed effect model for repeated measure for comparing GS-5745 to placebo cohorts. Estimated least square means and 90% confidence intervals (CI) of the changes from baseline will also be reported for each cohort as well as for difference between GS-5745 and placebo cohorts.

Analysis for other biomarkers and additional exploratory analyses will be discussed in Biomarker Analysis Plan (BAP).

8.10. Sample Size

A sample size of 25 evaluable subjects per arm for Part 1 and Part 2 will provide 80% power to detect a difference of 5% in percent predicted FEV₁ absolute change from Baseline between GS-5745 active treatment and placebo with a 2-side alpha level of 0.1 assuming a common SD of 7% {[Brouwer et al 2014](#), [Ramsey et al 2011](#), [Retsch-Bogart et al 2009](#)}. To compensate for early drop out, 30 subjects per arm will be enrolled assuming an attrition rate of 15%.

With respect to the sub-study in FRI, a sample size of 15 subjects on GS-5745 and 15 subjects on placebo provides more than 90% power to detect a 6% difference between the GS-5745 and placebo arms in FRI change from Baseline based on a 2 sample t-test at a 2-sided alpha level of 0.1. The calculation assumes SD of FRI change being 5% for the GS-5745 arm and 2% for the placebo arm as the FRI response is expected to be more heterogeneous in the treatment group.

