A sample size of 25 evaluable subjects per arm for Part 1 and Part 2 will provide 80% power to detect a difference of 5% change from Baseline in percent predicted FEV₁ between GS-5745 active treatment and placebo with a 2-sided alpha level of 0.1 assuming a common standard deviation (SD) of 7% {[Brouwer et al 2014](#), [Ramsey et al 2011](#), [Retsch-Bogart et al 2009](#)}. To compensate for early drop out, 30 subjects per arm will be enrolled assuming an attrition rate of 15%.

With respect to the sub-study in FRI, a sample size of 15 subjects on GS-5745 and 15 subjects on placebo provides more than 90% power to detect a 6% difference in FRI measurements (approximating an absolute change of 3% in FEV1) between the GS-5745 and the placebo arms in FRI change from Baseline based on a 2-sample t-test at a 2-sided alpha level of 0.1. The calculation assumes the SD of FRI change being 5% for the GS-5745 arm and 2% for placebo arm, as the FRI response is expected to be more heterogeneous in the treatment group. To compensate for early drop out, up to 35 subjects in Part 1 and up to 52 subjects in Part 2 will be enrolled assuming an attrition rate of 15%.

DMC Meetings

A total of 4 scheduled DMC meetings will occur throughout Part 1 and prior to the end of Part 2 of the study.

- Part 1: Safety Analysis #1 after 10 subjects have completed Week 2 Visit or early discontinued from the study
- Part 1: Safety Analysis #2 after 30 subjects have completed Week 8 Visit or early discontinued from the study
- Part 1: Safety Analysis #3 and Interim Efficacy Analysis after all randomized subjects have completed Week 8 Visit or early discontinued from the study
- Part 2: Safety Analysis #4 after 45 subjects have completed Week 8 Visit or early discontinued from the study

The detail is outlined in Section 8.11 with the corresponding GO/NO GO decision criteria.

This study will be conducted in accordance with the guidelines of Good Clinical Practice (GCP) including archiving of essential documents.

GLOSSARY OF ABBREVIATIONS AND DEFINITION OF TERMS

ABPA	allergic bronchopulmonary aspergillosis
ADA	anti-drug antibodies
AE	adverse event
ALT	alanine transaminase
AST	aspartate transaminase
ATS	American Thoracic Society
BAL	bronchoalveolar lavage
CBC	complete blood count
CF	cystic fibrosis
CFU	colony forming units
CFQ-R	Cystic Fibrosis Questionnaire – Revised
CFR	Code of Federal Regulations
CFTR	CF transmembrane conductance regulator
CI	confidence interval

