3.2. Study Design

This is a phase 2b, randomized, double-blind, placebo-controlled, multiple-center, multiple dose study.

The study is comprised of 2 parts. Part 1 will enroll 60 subjects in a 1:1 ratio to receive either 600 mg GS-5745 SC or placebo in a blinded manner for 8 weeks. Safety and efficacy analyses will be performed for Part 1 after all subjects have completed the Week 8 visit or discontinued from the study. If the FEV₁ percent predicted change combined with other endpoints indicate positive signals and the DMC determines there are no significant safety signals, then advancement to Part 2 will occur. Refer to Section 8.11 for more information.

Part 2 will enroll 90 subjects in a 1:1:1 ratio to receive SC injections of either 300 mg GS-5745, 150 mg GS-5745, or placebo for 8 weeks in a blinded manner. Visits and procedures for both Part 1 and Part 2 will be the same.

The FRI sub-study will require 2 FRI scans, one at Baseline and 1 at the Week 8 visit. A sub-set of study sites will be trained in FRI. All subjects enrolling into the study at those sites will participate in the FRI sub-study until approximately 30 subjects in Part 1 and up to 52 subjects in Part 2 have enrolled into the sub-study and completed Week 8. See Section 6.3.10 for additional information on FRI.

There will be a sputum cytology sub-study for both Part 1 and Part 2. A select sub-set of sites will perform sputum cytology from induced sputum samples to investigate changes in total cell count and cell count differential in sputum. No additional procedures will be required of subjects participating in the sputum cytology sub-study.

Blood samples for PK will be obtained at select scheduled study visits. PPD

[figure not shown]

Figure 3-1. Study Design

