8.11. Data Monitoring Committee

An independent multidisciplinary DMC will review the progress of the study and perform interim reviews of safety data. A total of 4 scheduled DMC meetings will occur throughout Part 1 and prior to the end of Part 2 of the study as outlined below.

Part 1: Safety Analysis #1

Because GS-5745 has not been administered previously to CF subjects, the DMC will review the unblinded safety data after 10 subjects (~5 active and ~5 placebo) have completed the Week 2 Visit or have prematurely discontinued from the study. Enrollment will continue during the DMC review process.

Part 1: Safety Analyses #2

The DMC will review the unblinded safety data after 30 subjects (~15 active and ~15 placebo) have completed the Week 8 Visit or have prematurely discontinued from the study. Enrollment will continue during the DMC review process.

Part 1: Safety Analyses #3 and Interim Efficacy Analysis

An interim efficacy and safety analysis will be performed when all 60 subjects (~30 active and ~30 placebo) have completed the Week 8 Visit or have prematurely discontinued from the study. The DMC and a select number of Gilead employees not directly involved in the study conduct will review the unblinded data.

With no safety concern, an estimated mean difference in absolute FEV₁% predicted between GS-5745 and placebo being $\geq 5\%$ may trigger the initiation of Part 2. If the mean difference is $< 2\%$, Part 2 may not be initiated. A comprehensive review of safety, FEV₁, FRI and other efficacy data including sputum MMP-9, CFQ-R, SNOT-22, TSQM, and CF exacerbation will be conducted before the decision is made to advance to Part 2 of the study. Enrollment of subjects into Part 2 of the study will be postponed until after the completion of the third DMC and unblinded Gilead review of the data.

Part 2: Safety Analysis #4

The DMC will review the unblinded safety data after 45 subjects (~ 15 in each treatment group) have completed the Week 8 Visit or have prematurely discontinued from the study. Enrollment will continue during the DMC review process.

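### Does the 80% power in Protocol 8.10 fail for the two Part 2 doses because 8.5 promises adjusted p-values?

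*Protocol*

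**What the plan says.** Protocol 8.10 gives a single power statement for both parts: "A sample size of 25 evaluable subjects per arm for Part 1 and Part 2 will provide 80% power to detect a difference of 5" percentage points in the absolute change of FEV1 percent predicted, "between GS-5745 active treatment and placebo with a 2-side alpha level of 0.1 assuming a common SD of 7" percent. It adds that "30 subjects per arm will be enrolled assuming an attrition rate of 15" percent. The synopsis repeats this ("with a 2-sided alpha level of 0.1 assuming a common standard deviation (SD) of 7" percent), and SAP 1.3 restates it in the past conditional.

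Part 1 has one comparison, 600 mg against placebo. For Part 2, Protocol 3.2 says "Part 2 will enroll 90 subjects in a 1:1:1 ratio to receive SC injections of either 300 mg GS-5745, 150 mg GS-5745, or placebo", so two doses share one control arm.

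Protocol 8.5 fits a separate MMRM to each part, with baseline FEV1 percent predicted as a covariate. One sentence, covering both parts, says that the differences from placebo "at Week 8 will be presented with the 90% confidence intervals (CIs) and adjusted p-values". Neither 8.5 nor the synopsis says what *adjusted* refers to, and neither names a multiple-comparison procedure.

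SAP 3.5 applies no multiplicity adjustment and gives the absence of inference as the reason. SAP 1.2 records that the study stopped after 6 subjects and that Part 2 was not initiated.

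**The concern.** With two doses tested against one placebo, a statistician's first thought on meeting adjusted p-values is multiplicity. The inputs in 8.10 leave no room for such an adjustment: 25 per arm is exactly what a single test at 0.10 needs. On that reading the protocol promises a stricter test in 8.5 than it powers for in 8.10, and each Part 2 dose would have less than the advertised chance of detection. The 90% confidence intervals, which are not described as adjusted, could also exclude zero while the adjusted p-value exceeded 0.10. If the p-values are not adjusted for multiplicity, 80% per dose holds, but the chance of at least one false positive in Part 2 is well above 10%. At stake is whether a reader can rely on the 80% for each lower dose.

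**Working it through.** **Inputs** (Protocol 8.10, repeated in the synopsis and SAP 1.3): n = 25 evaluable per arm, difference 5, common SD 7, two-sided alpha 0.10, attrition 15%.

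**Step 1: reproduce the stated figure.**
- Standard error of a difference = 7 × √(2/25) = 1.980.
- Noncentrality = 5 / 1.980 = 2.525.
- Normal approximation: Φ(2.525 − 1.645) = Φ(0.880) = 81.1%.
- Noncentral t: 80.1% with 48 df (two arms) and 80.4% with 72 df (three arms pooled).
- Enrolment: 25 / 0.85 = 29.4, rounded up to 30.

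The smallest n per arm that reaches 80% by noncentral t is 25. The stated figure is right for one comparison at 0.10, and so for Part 1 and for each Part 2 dose tested at 0.10.

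**Step 2: suppose the two Part 2 doses are adjusted to a familywise two-sided 0.10.**
- Bonferroni tests each dose at 0.05. The normal approximation gives Φ(2.525 − 1.960) = 71.4%; noncentral t with 72 df gives 70.3%.
- Dunnett (correlation 0.5, 72 df) has critical value 1.946, which gives 71.9%.
- The stepwise methods were simulated with a shared placebo arm.

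The 30-per-arm column is an upper bound in which every enrolled subject contributes fully: SE = 7 × √(2/30) = 1.807, 87 df.

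| Power per dose, true difference 5 | 25 per arm | 30 per arm |
|---|---|---|
| Unadjusted | 80.4% | 86.4% |
| Bonferroni | 70.3% | 78.1% |
| Dunnett | 71.9% | 79.5% |
| Holm, both doses effective | 76% | 83% |
| Hochberg, both doses effective | 78% | 84% |
| Holm or Hochberg, one dose effective | 71% | 78–79% |
| Fixed sequence, both effective: first / second dose | 80% / 69% | 86% / 78% |

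With both doses effective and 25 per arm, the chance of detecting at least one is 84% to 86% under Bonferroni, Holm, Dunnett or Hochberg. For 80% per dose, Dunnett needs 31 evaluable per arm and Bonferroni 32.

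**Step 3: adjusted p-values beside unadjusted 90% intervals.** At 25 per arm, the interval for an effective dose excludes zero while the adjusted p-value exceeds 0.10 in 80.4 − 71.9 ≈ 8.6% of trials (Dunnett; 8.56% before rounding) or 80.4 − 70.3 ≈ 10.2% (Bonferroni; 10.17% before rounding).

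**Step 4: suppose there is no multiplicity adjustment.** If neither lower dose works and Part 2 runs, the chance of at least one false positive is about 17.5% two-sided, or 8.7% in the direction of benefit. This is conditional on Part 2 running. Protocol 8.11 makes that step discretionary (below a 2-point difference, "Part 2 may not be initiated"), so the documents fix no unconditional figure for Part 2.

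**Step 5: which reading do the documents support?**
- For covariate adjustment: the sentence in 8.5 also covers Part 1, where a multiplicity adjustment would do nothing; the model has a baseline covariate; and the 90% intervals match 0.10 per comparison.
- For multiplicity: Part 2 has two doses, and SAP 3.5 links the absence of multiplicity adjustment to the absence of inference.

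Neither set is decisive. Adjustment over a family of one is harmless, so covering Part 1 does not rule out multiplicity. SAP 3.5 explains why nothing is adjusted now and does not say what the protocol had intended.

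**The case for a change.** The best case for a change is that the gap is real and cheap to close. Multiplicity is an ordinary meaning of adjusted p-values when two doses are tested, and no common procedure keeps 80% for both doses at 25 per arm. SAP 1.3 also carries the same sentence, Part 2 included, into the plan behind the synoptic report. A few sentences would remove the doubt.

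The arithmetic in that case stands, and so does the observation that the word is undefined. The step from there to an error in 8.10 does not. That section states power for a pairwise comparison at 0.10 and is correct for it; it claims neither familywise control nor joint power for both doses. Controlling familywise error across two doses in a Phase 2b study at 0.10 is a design choice, and the protocol nowhere commits to it.

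The shortfall is also uncertain in size. The efficacy set is "all subjects who were randomized into the study and received at least 1 dose of study drug", so subjects who drop out contribute their earlier visits to the MMRM, and baseline adjustment would tend to raise power. The documents do not quantify either effect. The 30-per-arm column shows that the loss could be small, or absent under Holm or Hochberg if both doses work.

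Finally, the proposed wording has nothing to act on. SAP 6.1.1 tests no hypothesis, so there is no method under which SAP 1.3 could restate Part 2 power.

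**Conclusion.** No change is called for. The 80% in Protocol 8.10 is correct as stated, at 80.1% to 80.4% for one active-versus-placebo comparison with 25 evaluable per arm. Under a multiplicity reading, per-dose power in Part 2 would be about 70% to 72% (Bonferroni, Dunnett), 76% to 78% (Holm, Hochberg, both doses effective), or 80% and 69% (fixed sequence). That reading is possible but not established. These figures assume a two-sample comparison with the stated SD of 7 and full data on 25 per arm.

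What is left is a missing definition that a statistician would normally settle in the SAP before Part 2 was analysed. Protocol 8.12 also left room for an amendment before Part 2 began. Part 2 was not initiated and the SAP is descriptive only, so no p-value or interval depends on the answer, and defining the word now would gain nothing.
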